4 STUDY DESIGN

4.1 Overview of Study

The study treatment consists of an open label 24-dose course of weekly subcutaneous (SQ) abatacept (Orencia) plus usual care, versus usual care subject comparators from the CARRA Registry to prevent the development of polyarthritis or uveitis, or initiation of systemic glucocorticoid, DMARD, and/or biologic medication within 12 months of enrollment in children with recent-onset limited JIA. Patients enrolled in the CARRA Registry receiving usual care who meet Limit-JIA inclusion/exclusion criteria will constitute the comparator arm, providing the proportion of children that develop disease extension on usual care alone.

There are 6 study visits: screening, enrollment, approximately month 3 (M3 visit), month 6 (M6 visit), month 9 (M9 visit), and month 12 (M12 visit [end of study]). The screening visit may be combined with the enrollment visit if all procedures can be completed and participant qualifies for the study. Clinical trial visits may occur either in person or via telehealth except for the screening or enrollment visits. One of these visits must be conducted in the clinic. The month 12 end of study visit must also be conducted in the clinic.

In order to enhance study recruitment and timely enrollment, a subset of Limit-JIA US based clinical trial sites will incorporate enhanced cohort identification of potential study participants that incorporates EHR-based algorithms to predict the presence of limited JIA. Specifically, a ‘computable phenotype’ will be utilized to generate screening lists of potentially eligible, recently diagnosed limited JIA patients who may be considered for enrollment. These EHR-based screening lists will then be further reviewed by site staff for study eligibility.

Study participant identification and enrollment using enhanced screening will be compared to use of traditional screening methods alone at this subset of sites. In addition, at a subset of US based sites, all enrolled CARRA Registry participants with JIA will have registry data supplemented by selected EHR data elements, which will be linked by the site and made available in the CARRA Data Warehouse, enabling analyses of registry data completeness.

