9 STATISTICAL ANALYSIS PLAN AND DETERMINATION OF SAMPLE SIZE

9.1 Statistical Design

The primary objective of LIMIT-JIA is to evaluate the effectiveness of a 24-dose course of abatacept (Orencia) plus usual care (including NSAIDs and/or intra-articular glucocorticoids) versus usual care alone, to prevent development of polyarthritis or uveitis, or initiation of treatment with other systemic medication(s) for JIA (i.e. one or more of the following: systemic glucocorticoids, DMARD or biologic) within 12 months of enrollment in children with recent-onset limited JIA.

Secondary objectives include comparison of participants and caregiver reported outcomes between the different treatment strategies.

The analysis population will include data from two parts of Limit-JIA. In Part I participants were randomly assigned to receive abatacept + usual care or usual care alone. Part II participants will all be assigned to receive abatacept + usual care.

Part I enrolled participants into a randomized open-label multicenter trial with a planned sample size of 306 JIA participants recruited from CARRA Registry sites. Participants were randomly allocated (1:1) to receive 24 weeks of abatacept plus usual care or usual care alone.

Randomization was stratified on uveitis risk (higher and lower) and polyarthritis risk (higher and lower). Upon completion of 24 weeks of randomized treatment, each participant was to receive usual care and undergo follow-up for assessment of outcomes for an additional 12 months.

Planned duration of the study for each participant was 18 months. Due to slow accrual and apparent loss of equipoise, enrollment into Part I has been discontinued 17February2022. As of October 29, 2021, 37 participants have been randomized in Part I. Part I participants will continue follow-up as planned.

Part II is a non-randomized continuation of LIMIT-JIA with planned enrollment of 80 evaluable participants receiving abatacept. Participants will receive 24 doses of abatacept plus usual care. Upon completion of 24 doses, each participant will receive usual care and undergo follow-up for assessment of outcomes for an additional 6 months. Planned duration of the study for each participant is 12 months. Part II will assess the efficacy of abatacept in prevention of disease extension by comparison of outcomes between participants enrolled in the abatacept arm and 428 CARRA Registry patients who would have met major eligibility criteria for LIMIT-JIA.

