9.2 Primary Analysis

The primary outcome is the proportion of participants experiencing disease extension, (development of polyarthritis or uveitis, or initiation of systemic medications during the 12-month period following enrollment). Participants will undergo evaluations for polyarthritis every 3 months during the 12-month duration of the study. Ophthalmological examinations for uveitis will be performed for enrolled participants according to the schedule in Table 3.

The primary analysis will compare the disease extension rate in the group of patients assigned to receive abatacept in Part II to a weighted average of disease extension rates observed in 6 cohorts (total of 428 patients) from the CARRA Registry who would have met the entry criteria for LIMIT-JIA. [See Appendix: Modification of Study Design and Rationale for Discontinuing Randomization to Control Arm]

The primary analysis will use the logistic regression model, $\log(\pi / (1 - \pi)) = \text{TRT}$, where TRT is the assigned treatment arm (abatacept or control). This analysis will test the null hypothesis that the disease extension rates in the abatacept and control arms are equal. The odds ratio with 95% confidence limits will describe the estimated treatment effect.

A secondary analysis of the disease extension rate will include a stratification factor for Part (I or II) and an interaction term (TRT x PART). This analysis will assess the homogeneity of treatment effect between Part I and Part II. Due to the small number of participants randomized to the control arm, statistical power to detect a TRT x PART interaction is limited.

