9.3 Major Secondary Analyses

Secondary analyses will be done for two study populations. Participants randomized in Part I or assigned to the abatacept arm in Part II will comprise the enrolled population [N approximately equal to 126 (37 Part I, 89 Part II)]. The overall study population [N approximately equal to 554] will include the enrolled population and 428 patients from the CARRA Registry whose disease extension results provided the control mean in Part II.

Secondary analyses for the enrolled population

Secondary analyses will generally be conducted as planned in Part I, although estimation of treatment effects or treatment by factor differences will be imprecise, since more than 80% of participants in the enrolled population are expected to receive abatacept.

Description of the time to disease extension will include cumulative incidence curves for the composite primary outcome and for the components disease extension, uveitis, and initiation of DMARDs or other biologic medication.

Descriptive analyses will summarize participant and caregiver reported outcomes (continuous outcomes of pain interference, fatigue, upper extremity function, mobility, anxiety, depression and global health PROMIS® modules, medication side effects (JAMAR), and the CHAQ). These outcomes will be measured at baseline and follow-up visits as shown in Table 5, and will be analyzed using a mixed model for repeated measures. Preliminary analyses will be performed to identify a parsimonious covariance structure among the repeated measures. The model will include as fixed effects treatment, time, treatment x time interaction, the baseline value of the outcome and the two stratification variables, the risk categories for polyarthritis and uveitis. Time will be treated as a categorical variable. The restricted maximum likelihood (REML) method of estimation and the Kenward-Roger degrees of freedom correction will be used. Contrasts will be constructed among the model parameters to test specific hypotheses. Overall treatment effect will be assessed by testing the null hypothesis of no treatment difference averaged over time. If the treatment x time interaction is significant at $\alpha=0.10$, additional descriptive tests may be done for treatment differences at specific time-points. Since more than 80% of participants in the enrolled population are expected to receive abatacept, there will be limited statistical power to determine treatment effects on these outcomes.

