Secondary analyses for the overall study population

Inclusion of data from 428 CARRA Registry patients may provide important information on the impact of treatment on time to disease extension and PROs. Since treatment assignment for the overall study population is not random, it is anticipated that causal inference techniques such as inverse probability or overlap weighting will be useful in determining the comparability of the Registry patients and participants enrolled in LIMIT-JIA.

The timing of evaluations for disease extension and PROs and missing data patterns are expected to differ between participants enrolled in LIMIT-JIA and CARRA Registry patients. Techniques such as multiple imputation may be used to enable modeling of the overall study population.

Details of the analysis of treatment effect for the overall study population will be provided in a separate SAP.

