9.4.2 Power, Sample Size and Type I error

The trial sample size was determined by the intended statistical comparison of the primary outcome (proportion of participants with disease extension) between the abatacept plus usual care and historical care usual care treatment arms [See Appendix: Modification of Study Design and Rationale for Discontinuing Randomization to Control Arm]. It is assumed that the proportion of participants with disease extension will be 34.3% in the usual care arm, and that

this rate will be reduced to 15% in the abatacept plus usual care arm. With 1-sided type 1 error = 0.025, 80 evaluable participants enrolled into the abatacept + usual care arm (compared with the historical control mean from 428 patients) would provide > 95% power using logistic regression. Assuming 10% of participants will not be evaluable, we will enroll up to 89 patients to receive abatacept + usual care arm. See Table 7. Hypothesis testing will be done with the Wald statistic testing the effect of the factor for treatment (abatacept + usual care, vs usual care) in the logistic model with factors for intercept and treatment.

Subgroup or other non-primary analyses may be done by inclusion of additional factors to the logistic regression model.

Table 7: Simulated power for sample sizes in the experimental arm of 10, 20, ..., 80; assuming type I error = 0.025 one-sided.

Sample size (evaluable) in experimental arm N =	Number to enroll assuming a 10% inevaluable rate	Power *
20	23	0.332
30	34	0.591
40	45	0.742
50	56	0.824
60	67	0.900
70	78	0.934
80	89	0.956

* For R_{ex} and R_c = disease extension rates in the experimental and control arms, resp. $H_0: R_{ex} = R_c = 0.343$ (estimated from the historical control group), and $H_1: R_{ex} < 0.15$ (i.e. $< R_c - 0.193$). Power was calculated by simulation of the logistic model, where extension rates followed a binomial distribution [$R_c = 0.343$, $N = 428$] in the control arm, and [$R_{ex} = 0.15$, N (for $N = 20, 30, \dots, 80$ as shown in the table)]. Type I error is 0.025, one-sided.

A sample size of eighty evaluable patients (all enrolled in the abatacept + usual care arm) will provide > 95% power to reject the null hypothesis that the disease extension rate is $\geq 34.3\%$ assuming one-sided type I error ≤ 0.025 and a true disease extension rate in the abatacept + usual care arm $\leq 15\%$. To allow for an inevaluable rate up to 10%, enrollment will be expected to be approximately eighty-nine patients.

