
9.5.4 Interim Analysis

Interim analyses, with stopping boundaries for futility and efficacy, are planned after approximately 40% ($n = 32$) and 80% ($n = 64$) of Part II participants have been followed for one year. Details will be provided prior to initiation of Part II.

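### The primary test compares non-randomised Part II children with historical Registry patients without adjustment, so a difference in baseline risk can pass for a drug effect or hide one

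*Combined protocol and SAP*

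**What the plan says.** Section 9.1 describes Part II as a non-randomised continuation in which everyone receives abatacept. Section 9.2 compares the Part II extension rate with a "weighted average of disease extension rates observed in 6 cohorts (total of 428 patients"). The model has one term, "where TRT is the assigned treatment arm (abatacept or control"). Section 9.4.2 confirms a Wald test in a "logistic model with factors for intercept and treatment", and allows further factors only in subgroup or other non-primary analyses.

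The plan recognises the issue elsewhere. Section 9.3, on the overall study population, begins a sentence "Since treatment assignment for the overall study population is not random" and foresees inverse-probability or overlap weighting for time to extension and PROs, with details left to a separate SAP. The secondary PRO model includes "the two stratification variables, the risk categories for polyarthritis and uveitis"; the primary model does not.

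The controls are described in three ways:
- Section 9.1: "428 CARRA Registry patients who would have met major eligibility criteria for LIMIT-JIA"
- Section 9.2: patients who would have met the entry criteria
- Section 4.1: Registry patients on usual care "who meet Limit-JIA inclusion/exclusion criteria will constitute the comparator arm"

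**The concern.** Without randomisation, a treatment-only model gives a drug effect only if the treated children, untreated, would have had the Registry's event rate. Meeting the same eligibility criteria does not ensure that, because the mix of risk within the criteria can differ. The protocol itself names reasons why it might:
- The Introduction says extension rates vary between studies and are higher in enthesitis-related and psoriatic arthritis.
- Section 4.3.3 lists ANA status and age at onset as risk factors for uveitis.
- Section 3.2 sets a minimum weight at Canadian sites only, which could shift age.
- Section 9.1 cites loss of equipoise as a reason for ending randomisation, so self-selection into treatment is possible.

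The phase 3 conclusion rests on this test. The bias could produce a false success or conceal a real effect, and enrolling more children would not remove it. The planned sensitivity analyses address missing 12-month outcomes (Section 9.2) and COVID-19 (Section 9.4), not confounding.

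**Working it through.** **Inputs (Section 9.4.2 and Table 7).** 80 evaluable treated and 428 controls; control rate 34.3%; treated rate 15%; one-sided type I error 0.025; stated power 0.956. The planned odds ratio is (0.15/0.85)/(0.343/0.657) = 0.338.

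**Method.** Enumerate every pair (x, y) of two independent binomials, x of 80 treated and y of 428 controls. Compute z = [ln(x/(80−x)) − ln(y/(428−y))] / √[1/x + 1/(80−x) + 1/y + 1/(428−y)], reject if z < −1.96, and sum the probabilities. This assumes a single look: Section 9.5.4 plans interim analyses "with stopping boundaries for futility and efficacy" but gives no boundaries.

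**The plan's own figures.** Power is 0.958 at N = 80 (stated 0.956) and 0.898 at N = 60 (stated 0.900). All seven rows of Table 7 agree within 2 points. With equal underlying risk the type I error is 0.022.

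**Shifted risk, no drug effect.** The Registry stays at 34.3%; the untreated risk in Part II is an assumption.

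| Untreated risk in Part II | Chance of declaring success |
|---|---|
| 40% | 0.2% |
| 35% | 1.7% |
| 34.3% | 2.2% |
| 34% | 2.5% |
| 32% | 5.3% |
| 30% | 10.2% |
| 28% | 18.0% |
| 25% | 35.8% |

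**Shifted risk, planned odds ratio 0.338.** The treated risk follows from odds = 0.338 × untreated odds. Power is 0.96 at an untreated risk of 34.3%, 0.93 at 36%, 0.83 at 40% (treated risk 18.4%) and 0.61 at 45% (treated risk 21.7%).

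**Tipping points.** 0.343 × 428 gives about 147 control events, with odds 147/281 = 0.523.
- 12/80: OR 0.337 (95% CI 0.177 to 0.643). Upper limit × Registry odds = 0.643 × 0.523 = 0.336, a risk of 0.336/1.336 = 25.2%. An observed 15% would no longer be significant if the true untreated risk was about 25%.
- 16/80: upper limit 0.856; 0.856 × 0.523 = 0.448, a risk of 30.9%.
- 18/80 is the largest count that succeeds (z = −2.06; 19/80 gives −1.84).

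**What adjustment does (illustration).** Assume two risk strata with untreated risks of 19.3% and 49.3%, and a Registry split evenly (mean 34.3%). In 1,500 simulated trials with 20% of Part II at high risk and no drug effect, false success was 33.7% unadjusted and 2.2% with the stratum in the model. With 80% at high risk and odds ratio 0.338, power was 64% unadjusted and 98% adjusted.

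**The Part I comparison as a check.** Assume the 37 Part I patients split 19/18, with risks of 15% and 34.3%. The SE of the log ratio of odds ratios is √(1/2.42 + 1/4.06 + 1/10.2 + 1/96.5) = 0.876, where each denominator is n·p·(1−p). For 80% power at two-sided 0.05 the ratio must reach exp(2.80 × 0.876) = 11.6.

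**The case against.** The strongest objection is that both Section 9.2 and Section 9.4.2 refer to an Appendix that is not in the text available here. It may describe the 6 cohorts and their weights; weights that reflect the trial's risk mix would adjust in part. That possibility stands. Against it, Table 7 simulates the control as a single binomial with N = 428, no covariate is named, and the stated model has treatment alone. The synopsis mentions enrolment stratified by baseline risk, but nothing available gives Part II stratum targets or links them to the Registry.

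Second, the plan has partial safeguards. The weighting in Section 9.3 extends to time to disease extension, and Section 9.4.1 tests homogeneity of effect across risk categories. The first is loosely specified and secondary. The second uses the enrolled population only and says nothing about comparability with the Registry. The treatment-by-Part analysis uses randomised controls, but Section 9.2 concedes limited power.

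Third, the risk shifts are hypothetical, and if 15% is observed the result survives unless untreated risk was about 9 points below the Registry. True; the exposure is greatest for more modest observed effects.

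Fourth, adjustment costs power, covers only measured factors, and does not remove bias from the differing evaluation schedules noted in Section 9.3. All correct. But where Part II risk is lower, the unadjusted test's higher power comes with an inflated error rate.

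**Conclusion.** The concern holds. As written, the primary test controls error at 2.5% only if the untreated risk of Part II children is about 34% or more, and delivers its stated power only if that risk is no higher than the Registry's. A shortfall of about 4 points (to 30%) raises false success to 10.2%; an excess of about 6 points (to 40%) cuts power to 0.83. These figures assume a single look, 80 against 428, and hypothetical risk shifts whose direction the available documents do not indicate. The reading that no adjustment is made rests on the stated model and Table 7; the 6-cohort weights remain unexplained. Because this is the decisive efficacy test, it must be fixed before the analysis goes ahead.

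**What to change.** Before any Part II outcome or interim analysis is examined:

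1. Make the primary analysis a pre-specified adjusted comparison with one stated estimand, for example the effect in the enrolled Part II children, with Registry patients propensity-weighted to the Part II case mix and robust variance.
2. Include at least the polyarthritis and uveitis risk categories (or the variables defining them), plus age at onset, ANA, joints affected and time since diagnosis where the Registry holds them for the 428.
3. State how the 6-cohort weighting fits with this.
4. Keep the treatment-only model as a sensitivity analysis, and add a tipping-point analysis for unmeasured confounding such as self-selection.
5. Reconcile the three descriptions of the controls.
6. State that the 0.956 power applies to the unadjusted model.

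The cost is SAP wording and modest analysis work with methods the plan already names. Registry covariate availability must be checked first, since Section 9.3 expects missing-data patterns to differ. The main downside is a smaller effective control sample. With assumed effective controls of 214, 150, 107 or 80, single-look power is about 0.93, 0.90, 0.86 or 0.82 at an untreated risk of 34.3%. If the weighted control risk were 25% and the odds ratio still 0.338, it would be about 0.84, 0.80, 0.75 or 0.70, so power should be restated for plausible case mixes.

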8 EFFICACY ASSESSMENTS

8.1 Primary Outcome

The primary outcome is the occurrence of any of the following: polyarthritis, active anterior uveitis, or initiation of systemic DMARDs and/or biologics, including systemic glucocorticoids (IV or PO) within 12 months of enrollment.

- (a) Polyarthritis is defined as a cumulative total of ≥ 5 active joints with arthritis since disease onset. The active joint count will be assessed at each study visit from baseline through month 12. Active arthritis is defined as joints with swelling not due to bony enlargement or joints with limitation of motion accompanied by either pain on motion and/or tenderness. For the purposes of counting affected joints, each toe counts as a single joint irrespective of whether it is the proximal interphalangeal joint (PIP), the distal interphalangeal joint (DIP), or both that are affected, consistent with previous clinical trials. Joint counts will be documented using a dedicated case report form (eCRF) at each study visit, tracking both specific joints and number of joints involved.⁶¹
- (b) The presence of active anterior uveitis, defined according to the Standardization of Uveitis Nomenclature for Reporting Clinical Data (SUN criteria) as the presence of one or more cells in each 1mm x 1mm slit beam field (Grade 0.5+, trace cells),⁶² will be assessed at standard of care ophthalmology visits as described by the Heiligenhaus modification of the American Academy of Pediatrics recommendations (see Table 2 in Section 4.3.1). Results will be collected using the existing CARRA Registry uveitis specific eCRF.
- (c) Use of systemic DMARDs and/or biologics, including systemic glucocorticoids (IV or PO) will be captured on the concomitant medication eCRF at each study visit.

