Statistical analysis of this study is planned upon study completion, when all participants in Part II have completed 12 months of follow-up or have withdrawn from the study.

Definition of analysis population will follow intention-to-treat (ITT) principles including, as much as possible, all enrolled participants evaluated for the outcome(s) being analyzed. An exception will be for safety analyses, wherein participants will be included corresponding to treatment actually received.

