For Parts I and II, the analysis population for the primary endpoint will consist of participants whose disease status is determined at 12 months. In case some participants are not evaluated at 12 months, sensitivity analyses may be performed including simulated data for the participants with unobserved primary outcome. Simulations will be conducted under a variety of assumptions about the distribution of the unobserved outcomes including 1) under the null hypothesis, 2) under alternative hypotheses unfavorable to the abatacept plus usual care treatment arm and, if appropriate, 3) according to plausible patterns determined by taking into account factors such as baseline disease status, length of follow-up, and magnitude and variance of estimated treatment effect from observed data. Non-random patterns of missing data may be considered. If the estimated treatment effects and conclusions from hypothesis testing are generally consistent between the primary and sensitivity analyses, the primary analysis will be considered accurate.

Methods used to account for missing data will be described in more detail in the Statistical Analysis Plan.

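### The primary set keeps early failures but drops children who leave event-free before month 12, a small bias that usually works against abatacept, and no missing-outcome sensitivity analysis is firmly required

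*Combined protocol and SAP*

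**What the plan says.** Section 8.1 defines a cumulative endpoint: polyarthritis, active anterior uveitis, or "initiation of systemic DMARDs and/or biologics, including systemic glucocorticoids (IV or PO) within 12 months of enrollment". Section 9.2 repeats the time window, "initiation of systemic medications during the 12-month period following enrollment". Section 9.2 then sets the primary population for both parts: "the analysis population for the primary endpoint will consist of participants whose disease status is determined at 12 months". For patients without a 12-month evaluation, "sensitivity analyses may be performed including simulated data for the participants with unobserved primary outcome". It lists scenarios under the null, under unfavourable alternatives, and under plausible patterns, and adds that "Methods used to account for missing data will be described in more detail in the Statistical Analysis Plan".

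The intention-to-treat statement in section 9.1 is qualified: "including, as much as possible, all enrolled participants evaluated for the outcome(s) being analyzed". Section 9.3 says that "missing data patterns are expected to differ between participants enrolled in LIMIT-JIA and CARRA Registry patients", and for the secondary analyses of the overall population it adds that "Techniques such as multiple imputation may be used to enable modeling of the overall study population". Section 9.4 does commit to sensitivity analyses of COVID-19 effects on the primary endpoint, missed visits among them. Section 9.4.2 plans 80 evaluable patients out of 89 enrolled, allowing for 10% unevaluable.

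**The concern.** An event at month 4 settles the outcome at month 4. Freedom from events is settled only at month 12. A rule that requires a determined status therefore makes inclusion depend on the outcome: among patients who leave early, failures stay and non-failures go. The 10% allowance protects the number analysed but not the estimate.

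The comparison is non-randomised, so equal loss in the two groups cannot be taken for granted, and section 9.3 itself expects missing-data patterns to differ. If the controls are complete, the trial rate is pushed up and abatacept is penalised. If the Registry loses more patients than the trial, the control rate is pushed up further and the test becomes too liberal. In the text available, the primary comparison states no rule for incomplete follow-up in the 428 controls, and the analysis that would show how much the missing outcomes matter *may* be done rather than *will* be done.

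**Working it through.** **Inputs from section 9.4.2:** control rate 34.3%, abatacept rate 15%, 80 evaluable against 428, one-sided 0.025, Wald test in a logistic model with treatment only, 89 enrolled. **Assumptions:** constant hazard over the 12 months, uniform dropout time, and the dropout percentages for each group other than the plan's 10%.

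**1. The plan's own figure.** Exact binomial enumeration of the one-sided Wald test gives power 95.8% (Table 7: 0.956) and type I error 2.2%. For enrolment, 80/0.90 = 88.9, so 89. The sample size is not in error.

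**2. Apparent rate.** Let p be the true 12-month rate, d the dropout proportion, and EF the chance of an event before a uniform dropout time. With λ = −ln(1−p), EF = 1 − p/λ.
- p = 0.15: λ = 0.1625, EF = 0.077.
- p = 0.343: λ = 0.4201, EF = 0.183.

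Apparent rate = [(1−d)p + d·EF] / [(1−d) + d·EF]. At d = 0.10:
- p = 0.15: (0.135 + 0.0077)/(0.9 + 0.0077) = 15.7%.
- p = 0.343: (0.3087 + 0.0183)/(0.9 + 0.0183) = 35.6%.

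At d = 5% and 20%, 15% appears as 15.3% and 16.6%, and 34.3% as 34.9% and 37.2%. At d = 10% and p = 0.15 the number analysed is 89 × 0.9077 = 80.8, so 80 is kept in the test calculations.

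**3. Operating characteristics with 10% trial dropout.** The same formula is applied to the Registry, and the same enumeration is run with 80 against 428.

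| Assumed Registry dropout | Type I error |
|---|---|
| 0% | 1.3% |
| 5% | 1.7% |
| 10% | 2.2% |
| 15% | 3.0% |
| 20% | 4.1% |

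Power with complete controls is 94.1%. Break-even is equal loss.

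**4. Tipping point.** Take 9 of 89 unevaluable and controls at 147/428 (0.343 × 428 = 146.8).
- 18/80: ln(18/62) − ln(147/281) = −0.589, SE 0.286, z = −2.056, p = 0.020.
- With 3 of the 9 failing, 21/89: −0.527, SE 0.270, z = −1.955, p = 0.0253, so significance is lost.
- With 3 of 9 failing, 17/80 and 16/80 stay significant (20/89, p = 0.0155; 19/89, p = 0.0091).
- The planned 12/80 is lost only if all 9 fail (12 + 9 = 21, again 21/89).

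The chance that a significant result at 80 is lost at 89, with controls fixed, is 0.5% at a true 15% and 3.5% at a true 20% if leavers fail like the others (0.9% and 4.0% change the other way). It is 4.1% and 12.2% if leavers fail at 34.3%.

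**5. Does the remedy work?** Trials of 89 against 428 were simulated under the null with 10% trial dropout. Type I error:

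| Registry dropout | Complete case | Imputation from treatment only | Imputation from a within-arm hazard |
|---|---|---|---|
| 0% | 1.3% | 1.2% | 2.3% |
| 10% | 2.5% | 2.3% | 2.4% |
| 20% | 4.1% | 4.1% | 2.3% |

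The complete-case and hazard columns come from 20,000 trials per setting, with 20 imputations and Rubin's rules; the treatment-only column comes from 6,000. Imputing from the treatment-only model leaves the bias, because it ignores how long each patient was event-free. The hazard model matches the simulated data, so its column is a best case.

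**The case against.** With complete controls the rule is conservative, and with equal loss there is no inflation. Every type I error above 2.5% on the ordinary reading needs Registry loss greater than trial loss. No available text gives Registry loss, and section 9.3 says that the patterns will differ without saying in which direction. Sections 9.2 and 9.4.2 also refer to an Appendix on the control group that was not available here and may deal with control follow-up. All of this stands and limits the point.

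Sensitivity analyses are not wholly optional either: section 9.4 commits to those for COVID-19, and section 9.2 lists null and unfavourable scenarios, a consistency rule, and further detail to come in the Statistical Analysis Plan. This stands in part. The COVID-19 commitment is narrower than all missing outcomes. The firm wording about simulations in section 9.2 follows the *may* sentence and describes how they would be run, not whether. The deferred detail does not change the primary set already fixed there.

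A reader might infer that early failures who then leave are dropped as well, which would favour abatacept. If 10% of failures only were lost (an assumption), 34.3% would appear as 0.343 × 0.9/(0.343 × 0.9 + 0.657) = 32.0%, with type I error about 5.3%. The documents do not support this as the intended rule: the sensitivity analyses are aimed at patients with an unobserved outcome, and an observed event is not unobserved. Table 2 footnote 1 names polyarthritis and uveitis among reasons for leaving the study, but section 6.4.5 sets no withdrawal criteria and sections 6.4 and 6.4.3 encourage or allow patients to stay, so the footnote is not a separate defect.

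**Conclusion.** The point holds as a minor to moderate weakness. The primary set conditions on outcome, nothing in the available text returns event-free leavers to the primary comparison, and no missing-outcome analysis is mandatory beyond COVID-19 effects. At the plan's own 10% loss the bias is about 0.7 percentage points at a true 15% (15.7% against 15%) and costs 1.7 points of power (95.8% to 94.1%) with complete controls.

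Two stronger conclusions do not follow. One is that the rule inflates type I error: that depends on an unknown, larger Registry loss. The other is that it contradicts intention to treat: section 9.1 limits that principle to patients evaluated for the outcome. At the expected 12/80 the conclusion survives unless all 9 unevaluable patients fail; results near 18/80 are the fragile ones. The sizes rest on a constant hazard, uniform dropout times and assumed Registry loss.

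**What to change.** 1. State in section 9.2 that any event observed by month 12 is a failure, whatever the later attendance.
2. Include all enrolled Part II patients in the primary comparison. First recover 12-month status from the Registry and medical records, which sections 6.4 and 10.3 leave open. For event-free patients still lost early, pre-specify multiple imputation that conditions on event-free follow-up time, for example a within-arm hazard model, and analyse the result with the planned logistic Wald test. A 12-month cumulative-incidence estimate is an alternative. Keep the complete-case analysis as a sensitivity analysis.
3. Apply the same rule to the 428 controls where event and last-contact dates exist. Otherwise report how their rates handled incomplete follow-up.
4. Change *may* to *will* for the sensitivity analyses, and add a tipping-point table to the scenarios already listed.

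The cost is a few sentences in section 9.2 and the Statistical Analysis Plan and a little more analysis. The primary result would then rest on a missing-at-random assumption, so the unfavourable scenarios are still needed, and equal treatment of the controls needs patient-level Registry dates. The rule should be settled before the first interim look in section 9.5.4.
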